### ***Recruitment to practitioner focus groups and interviews***

The RA will identify a suitable date and location at participating sites. Details will be sent to clinicians who registered interest in attending. The aim will be to ensure a mix of surgeons, neonatologists, specialist nurses and dieticians from across participating sites are invited to attend each group. The option to conduct the focus groups online will be available due to the COVID 19 pandemic. For clinicians unable to attend, we will conduct up to 10 telephone interviews.

### ***Informed consent***

## **Telephone interviews**

The RA will begin the telephone interview by confirming with the person they are calling that it is the intended participant, before explaining the aims of the study, providing an opportunity for questions and verbally obtaining informed consent for the study. The PIS will have been emailed or posted to the participant in advance for them to read. The RA will read each aspect of the consent form to participants, including consent for audio recording and to receive a copy of the findings when the study is complete. The RA will tick each box on the consent form when the participant provides verbal consent. After the interview is complete the RA will sign the consent form and send a copy to the participant.

## **Focus groups**

The RA will seek written informed consent for the study using the ToSCiN Practitioner Consent Form. The participant and the researcher will sign the consent form. If online focus groups are used (due to the COVID-19 pandemic), electronically signed consent forms will be requested from all participants via email before the scheduled focus group. The Practitioner Information Sheet will be sent to all participants by email or post. The RA will then check that participants have had enough time to read the PIS and whether they have any questions. They will then email a copy of the consent form to each participant. Participants will complete and return the consent form, either by printing out, signing, and scanning a copy, or by typing their name and signature into an electronic copy.

## ***Interview and focus group conduct***

The RA will check that the parent has had sufficient time to read the ToSCiN Participant Information Sheet. Topic guides will be informed by early WS 1 and early WS 2.1 findings as well as trial feasibility and design in HTA funded studies (FiSh, Fever and EcliPSE).[13,14]

Respondent validation will be used so that previously unanticipated topics will be added to the topic guides and discussed with participants as further interviewing and analyses progress. Interviews will be conducted until data saturation is reached (no new themes are emerging in the analysis of data). Based on previous feasibility studies we anticipate interviewing 15-25 parents, a focus group at each participating site and up to 10 telephone interviews with practitioners unable to attend a focus group.

At the end of the interview a £30 Amazon voucher will be given to the participant to thank them for their time. A ToSCiN Study Participant thank you letter will be posted to participants after the interview, including a copy of the consent form.

Interviews will be recorded using an Olympus digital audio recorder. Audio files and transcripts will be stored in encrypted files on a University of Liverpool drive only accessible to [name] and the RA. Audio files will be deleted after they have been transcribed and the transcriptions checked by [name] and the RA.

#### **4.6. WS 2 Data Analysis**

[name] and the RA will carry out analysis of anonymised data from the interviews, questionnaires and focus groups using NVivo 10 qualitative data analysis package. WS 2.1 clinical data will be summarised descriptively and will complement the data analysed in WS 3 to provide an overall picture of the demographic and clinical features of infants with a stoma to inform a potential future trial population. Furthermore, by interrogating these clinical data alongside the responses to clinician surveys and parental interviews, we will be in a position to understand which demographic and clinical features are likely to influence both clinician and parental decision-making regarding suitability for a future trial.

Data from WS 2.2 questionnaires will be summarised in key patient groups and time points so that an assessment can be made of broadly what groups of infants' clinicians would be happy to recruit to a trial, at what time points and which factors contribute to these opinions.

WS 2.3 interviews and focus groups will be transcribed, checked and anonymised as the study progresses. QSR NVivo software will be used to assist in the organisation and indexing of qualitative data. Thematic analysis will be informed by the constant comparison approach of grounded theory, the focus will be modified to fit with the criterion of catalytic validity, whereby findings should be relevant to future research and practice (i.e. the design of the proposed ToSCiN RCT). Findings from the interviews and focus groups will be fed into the design (including patient information materials), approach to consent and training for site investigators.

## **5. WORK-STREAM 3: ANALYSIS OF THREE EXISTING NATIONAL DATABASES**

### **5.1. Overall work-stream design**

Analyses of 3 existing databases will be carried out in order to generate quantitative data that will address the following study objectives: establishing current UK practice, defining a population for trial inclusion and providing the number of eligible infants; establishing appropriate trial design and outcome measures; and assessing suitability of using routinely collected data for a future trial.

Analyses will be guided by the results of the clinician survey in WS 1. The survey will indicate which patient factors and clinical outcomes are required to be known in order to design a trial: these data can then be extracted from the three databases. Once it is known which infants clinicians consider to be appropriate for trial inclusion, these complementary databases can be used together to calculate the potential number of eligible infants available for inclusion: Hospital Episode Statistics (HES) will provide denominator data for the total number of infants with a stoma, National Neonatal Research Database (NNRD) will provide the granularity required to deduce the proportion of those who have the clinical characteristics for a trial. The databases will not be linked and analyses will proceed separately.

### **5.2. Data sources**

#### ***The National Neonatal Research Database (NNRD)***

The NNRD holds data from all infants admitted to National Health Service (NHS) neonatal units in England, Scotland and Wales (approximately 80,000 infants annually; 8,000 less than 32 weeks gestation); all NHS neonatal units in England and Wales have been contributing data to the NNRD since 2012.[15]

Contributing neonatal units are known as the UK Neonatal Collaborative (UKNC). Data are extracted from point-of-care neonatal electronic health records completed by health professionals during routine clinical care. A defined data extract, the Neonatal Dataset of approximately 450 data items, is transmitted quarterly to the Neonatal Data Analysis Unit at Imperial College London and Chelsea and Westminster NHS Foundation Trust where patient episodes across different hospitals are linked and data are cleaned (queries about discrepancies and implausible data configurations are fed back to health professionals and rectified). Data items include demographic and admission items (e.g. maternal conditions,

gestation, birth weight), daily items (e.g. respiratory support, medication, surgery, feeding information), discharge items (e.g. feeding and weight at discharge) and ad hoc items (entered if and when they occur, e.g. suspected infection, ultrasound scan findings, abdominal x-ray findings).

### ***The British Association of Paediatric Surgeons Congenital Anomalies Surveillance System (BAPS-CASS)***

BAPS-CASS has been the UK's principal data collection system with which to study the surgical management of a range of neonatal conditions on a population basis.[16] It has conducted a number of prospective, multi-centre cohort studies over the past 10 years. Two of these were of infants with conditions that frequently require stoma formation: necrotizing enterocolitis and meconium ileus.

### ***Hospital Episode Statistics (HES)***

Hospital Episode Statistics (HES) is a database containing details of all admissions, emergency department attendances and outpatient appointments at NHS hospitals in England. Data are collected during a patient's time at hospital as part of the Commissioning Data Set (CDS). This is submitted to NHS Digital for processing and is returned to healthcare providers as the Secondary Uses Service (SUS) data set and includes information relating to payment for activity undertaken. It allows hospitals to be paid for the care they deliver. This data can also be processed and used for non-clinical purposes, such as research and planning health services, because these uses are not to do with direct patient care, they are called 'secondary uses'.

## **5.3. Database analyses**

### ***The National Neonatal Research Database (NNRD)***

Analyses will be carried out by researchers at the Neonatal Data Analysis Unit (NDAU) at Imperial College London where the database is hosted. These activities will be led by co-investigator [name] and her team will access and analyse the data. Pseudo-anonymised data will be extracted for infants born and admitted to neonatal units in England and Wales over a six-year period between 2014 and 2019 inclusive. Data for infants with a stoma will be verified with host centres.

### **Inclusion criteria**

Eligible infants of any gestational age within the NNRD who had a stoma formed during neonatal care in England and Wales.

## **Exclusion criteria**

Infants with anorectal malformations and Hirschsprung's will be excluded because stoma closures in these infants are usually part of a planned treatment pathway. Data from Scotland will be excluded.

## **Outcomes**

The primary outcome of the study is time to stoma closure defined as days from initial stoma formation.

We will also determine the following outcomes (as well as any others felt to be important in the clinician survey WS 1): survival; length of hospital stay; duration of parenteral nutrition (PN); time to full enteral feeds; growth; complications of surgery; other adverse events; days of invasive ventilation post-operatively; sepsis; necrotising enterocolitis; chronic lung disease/bronchopulmonary dysplasia (preterm only); brain injury on imaging; retinopathy of prematurity (preterm only).

## **Statistical Analysis**

Descriptive results will be presented using means (standard deviations) or medians (interquartile ranges) for continuous variables and proportions for categorical variables. For comparisons between different subgroups of infants, the Chi-squared test will be used for categorical data and the t-test or Wilcoxon rank-sum test for continuous variables. Regression analysis will be used to explore factors associated with timing of stoma closure.

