### ***Hospital Episode Statistics (HES)***

HES data will be analysed by co-investigator [name] via an anonymised, linked dataset (single record for each individual) for 10 years (2006-2016). The data will be stored on a secure encrypted server and will be accessible only by [name]. Using OPCS codes for stoma formation and age under 4 weeks (corrected for gestation using maternal data ‘tail’), we will establish the number of infants that underwent stoma formation in the neonatal period. ICD-10 codes will be used to establish their primary diagnoses and the timing of stoma closure will be established using OPCS codes. Other outcomes such as death in hospital prior to closure, death before 1 year; LOS (total for that period), operations within 28 days; death within 28 days of operation, total length of stay in hospital in first year of may also be collected if deemed to be important by the results of the survey (WS 1).

These data will provide an overview of current practice and an indication of the number of infants in England eligible for inclusion in a trial. Importantly it will allow us to capture timing of stoma closure for those discharged from the neonatal unit prior to this and hence missed by NNRD.

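### The summaries and tests named for the NNRD primary outcome, time to stoma closure, make no allowance for infants discharged with a stoma or dying before closure

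*Protocol*

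**What the plan says.** All references are to the Protocol.

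- **Outcome (5.3, NNRD, Outcomes):** "The primary outcome of the study is time to stoma closure defined as days from initial stoma formation". Survival is listed separately and is not tied to the closure analysis.
- **Population (5.3, NNRD, Inclusion criteria):** "Eligible infants of any gestational age within the NNRD who had a stoma formed during neonatal care in England and Wales". Entry depends on formation of a stoma, not on its closure.
- **Summaries (5.3, NNRD, Statistical Analysis):** "Descriptive results will be presented using means (standard deviations) or medians (interquartile ranges) for continuous variables".
- **Subgroup comparisons and regression (same place):** "the t-test or Wilcoxon rank-sum test for continuous variables. Regression analysis will be used to explore factors associated with timing of stoma closure". The type of regression model is not given.
- **Missing data (5.3, NNRD):** covers infants moved to surgical centres that do not contribute to NNRD, expects most of them to come back to a neonatal unit, and promises verification of stoma cases with host centres. It does not mention discharge with a stoma or death.
- **HES (5.3):** one stated purpose of HES is to "capture timing of stoma closure for those discharged from the neonatal unit prior to this and hence missed by NNRD". The list opening "Other outcomes such as death in hospital prior to closure" is optional and depends on the Work-stream 1 survey.
- **Linkage and coverage:** 5.1 rules out linkage between the databases. NNRD covers England and Wales, 2014 to 2019 (5.3). HES covers England (5.2), 2006 to 2016 (5.3).

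No section mentions censoring, a survival method or competing risks.

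**The concern.** Days to closure is an event time. For an infant who goes home with a stoma, NNRD shows only that closure took longer than the time to discharge. For an infant who dies first, there is no closure time at all. A mean, median, t-test or Wilcoxon test has no place for either kind of record. The natural result of using them is an analysis of infants whose closure was seen, which selects the shorter closure times.

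Section 5.4 uses these results to identify factors linked with early or late closure, gestation and diagnosis being its examples, and from there to help define the trial population and perhaps inform a sample size. Section 6 takes them to the design meeting, where the timing of the two arms is to be agreed. Gestation and diagnosis plausibly also affect length of neonatal stay. A group that leaves the unit sooner would then appear to have its stomas closed sooner, even where true timing is the same.

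**Working it through.** The NNRD section gives no expected closure time, event count or sample size, so there is no plan figure to reproduce. The check is an illustration by simulation (400,000 infants).

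**Inputs from the document.** Section 2.1 reports closure times of 27–394 days (n=34) and 21–469 days (n=76). It also confirms that some infants are discharged before closure, without giving the share.

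- Geometric midpoints: √(27 × 394) = 103 days; √(21 × 469) = 99 days.
- Log-SD = ln(max/min) ÷ expected range of n standard normal values, which gives 0.64 and 0.65.
- Used: lognormal closure time, median 100 days, log-SD 0.65.

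**Assumptions not in the documents.** Discharge is lognormal, independent of closure, with log-SD 0.5 and median 75 to 200 days. Deaths, where included, are early (exponential, mean 30 days).

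**Step 1: share discharged with a stoma, no deaths.** P(discharge before closure) = Φ[ln(100/m) ÷ √(0.65² + 0.5²)] = Φ[ln(100/m) ÷ 0.820], where m is median discharge. For m = 75 this is Φ(0.351) = 64%. For m = 100, 150 and 200 it is 50%, 31% and 20%. The simulation agrees.

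**Step 2: median among closures seen, no deaths.**

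| Median discharge (days) | Discharged with a stoma | Observed-only median | Kaplan-Meier median |
|---|---|---|---|
| 75 | 64% | 60 | 100 |
| 100 | 50% | 68 | 100 |
| 150 | 31% | 79 | 100 |
| 200 | 20% | 86 | 100 |

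The observed-only median is too early by 100 − 86 = 14 to 100 − 60 = 40 days. Censoring at discharge recovers the true value, as it must when discharge is independent of closure.

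**Step 3: subgroups with identical true closure times.** With median discharge at 150 against 75 days, the observed-only medians are 79 and 60 days. With 120 against 60 days they are 73 and 54. Each gap of 19 days comes entirely from the difference in discharge time.

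**Step 4: deaths only, no discharge.**

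| Dying before closure | Observed-only median | Day by which half of all infants have closed |
|---|---|---|
| 9% | 99 | 108 |
| 18% | 99 | 119 |
| 28% | 97 | 135 |

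Deaths move the observed-only median by 1 to 3 days. What is lost is the share who ever close: at most 91%, 82% and 72% here, against 100% by construction among observed closures.

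**Can HES complete the NNRD outcome?** No. Without linkage, a HES closure date cannot be attached to an NNRD infant. The two sources also share only England and 2014 to 2016.

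**The case against.** Five points on the other side have substance.

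1. *Nothing says that unclosed infants are dropped.* A reader might infer that the protocol treats closure as fully observed. It does not say so. The wording on continuous variables is generic and serves the whole outcome list. This stands as a limit: the exclusion is inferred from the methods named. But no other class of method is offered for an outcome in days.
2. *The regression may already be right.* The sentence on timing of closure fits a Cox or competing-risk model, and an analysis plan that is not at hand may say so. This stands. The point rests on the summaries and tests, not on the regression.
3. *The gap is recognised and partly covered.* HES is there to capture later closures and holds diagnosis and gestation. BAPS-CASS records timing of closure, and host-centre verification might recover some dates. Together these describe later closures, but none is stated to complete the NNRD outcome or its subgroup comparisons.
4. *Transfer is not discharge.* A reader might count every transfer as lost. NNRD links episodes across hospitals (5.2) and most transferred infants are expected back, so the documents support this only for infants permanently lost from NNRD.
5. *The stakes are limited.* This is a descriptive feasibility study. Section 5.1 does not list defining early and late closure among the aims of Work-stream 3. The survey and focus groups address that, and section 6 settles it on all the evidence. NNRD contributes to the definition but does not fix it.

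**Conclusion.** The concern holds for the summaries and subgroup tests of the NNRD primary outcome. They suit fully observed values, while the protocol itself acknowledges that closures after discharge are not in NNRD and plans no linkage that could supply them.

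The size of the bias is unknown. The figures of 60 to 86 days against 100 rest on the assumed closure and discharge distributions and on discharge being independent of closure. The direction, towards earlier closure, also holds if infants sent home close later on average than those closed in the unit. Discharge related to planned timing could change the size, and in principle the direction, which is why a check against HES is needed.

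A reader might go further and say that deaths also make closure look too early. The calculation does not support this: the observed median moves by 1 to 3 days, and the harm is an overstated share reaching closure.

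Severity is moderate. The analysis is descriptive and one input among several, but it is the stated primary outcome and is easily put right.

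**What to change.** In 5.3, NNRD, Statistical Analysis:

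- Summarise time to closure by cumulative incidence from stoma formation (Aalen-Johansen), with death before closure as a competing event.
- Censor infants discharged with a stoma, or permanently lost from NNRD, at their last known date. Keep transferred and repatriated infants in follow-up, and use any closure dates recovered through host-centre verification.
- State that the regression for timing is cause-specific Cox or Fine-Gray, and do not use the t-test or Wilcoxon test for time to closure.
- Report the percentage discharged with a stoma, by subgroup.
- Because discharge may be informative, compare the NNRD curve with HES for England in 2014 to 2016, with the age at stoma formation and the diagnostic exclusions aligned.

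In 5.3, HES: make death before closure a required item, and censor at the end of available data.

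The cost is protocol wording, standard survival code and slightly more analysis, largely on dates already held. The downside is reliance on independent censoring at discharge, which the HES comparison can probe but not prove.

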## **Missing data**

We expect missing data from infants that are transferred to surgical centres not co-located within a neonatal unit as they do not submit data to NNRD. These include Great Ormond Street Hospital, Sheffield Children's Hospital, Birmingham Children's Hospital, Alder Hey Children's Hospital. However, we expect that the majority of infants should be repatriated back to neonatal units for post-surgical management.

To maximise data completeness and accuracy, we will verify data for infants with a stoma with host centres.

## ***The British Association of Paediatric Surgeons Congenital Anomalies Surveillance System (BAPS-CASS)***

Analyses of data from two previous studies (stored on a secure encrypted server) will be carried out by co-investigators at the University of Oxford. The study on necrotising

enterocolitis (NEC, 2013-14) comprised 236 infants (159 had a stoma) and the study on meconium ileus (2014-2016) comprised 72 infants (21 had a stoma) will be used for this purpose.[16] These cohorts will be reviewed to determine factors including: (i) background characteristics e.g. sex, gestation and birth weight; (ii) operative details e.g. age, findings, type/position of stoma and remaining bowel length; (iii) operative complications including wound infection, adhesive obstruction, stoma ‘complications’ and need for reoperation within 28 days; (iv) timing of stoma closure; and (v) clinical outcomes e.g. need for parenteral nutrition at 28 days, length of stay and death during hospital stay.

### ***Hospital Episode Statistics (HES)***

HES data will be analysed by co-investigator [name] via an anonymised, linked dataset (single record for each individual) for 10 years (2006-2016). The data will be stored on a secure encrypted server and will be accessible only by [name]. Using OPCS codes for stoma formation and age under 4 weeks (corrected for gestation using maternal data ‘tail’), we will establish the number of infants that underwent stoma formation in the neonatal period. ICD-10 codes will be used to establish their primary diagnoses and the timing of stoma closure will be established using OPCS codes. Other outcomes such as death in hospital prior to closure, death before 1 year; LOS (total for that period), operations within 28 days; death within 28 days of operation, total length of stay in hospital in first year of may also be collected if deemed to be important by the results of the survey (WS 1).

These data will provide an overview of current practice and an indication of the number of infants in England eligible for inclusion in a trial. Importantly it will allow us to capture timing of stoma closure for those discharged from the neonatal unit prior to this and hence missed by NNRD.

